APPENDIX C: Global Pomalidomide Pregnancy Prevention Plan

Global PPP Pomalidomide Adult
Celgene Corporation

Protocol [#]
Version 4.0 Approved: 30 October 2014
Effective Date: 19 December 2014

1. POMALIDOMIDE PREGNANCY PREVENTION PLAN FOR SUBJECTS IN CLINICAL TRIALS

The Pregnancy Prevention Plan (PPP) applies to all subjects receiving pomalidomide within a clinical trial. The following PPP documents are included:

1. The Pomalidomide Risks of Fetal Exposure, Pregnancy Testing Guidelines and Acceptable Birth Control Methods document (Section 2) provides the following information:
 - Potential risks to the fetus associated with pomalidomide exposure
 - Definition of female of childbearing potential (FCBP)/female not of childbearing potential (FNCBP)
 - Requirements for counseling of all subjects receiving pomalidomide about pregnancy precautions and the potential risks of fetal exposure to pomalidomide
 - Acceptable birth control methods for both female subjects of childbearing potential and male subjects receiving pomalidomide in the study
 - Pregnancy testing requirements for subjects receiving pomalidomide who are FCBP
2. The Pomalidomide Education and Counseling Guidance Document for each gender (female and male; Section 3 and Section 4 respectively) must be completed and signed by a trained counselor at the participating clinical center prior to each dispensing of pomalidomide. A copy of this document must be maintained in the subject's records for each dispense.
3. The Pomalidomide Information Sheet (Section 5) will be given to each subject receiving pomalidomide. The subject must read this document prior to starting pomalidomide and each time the subject receives a new supply of pomalidomide.

2. POMALIDOMIDE RISKS OF FETAL EXPOSURE, PREGNANCY TESTING GUIDELINES AND ACCEPTABLE BIRTH CONTROL METHODS

2.1. Risks Associated with Pregnancy

Pomalidomide was teratogenic in both rats and rabbits when administered during the period of organogenesis. Pomalidomide is an analogue of thalidomide. Thalidomide is a known human teratogen that causes severe life-threatening human birth defects. If pomalidomide is taken during pregnancy, it can cause birth defects or death to an unborn baby.

The teratogenic effect of pomalidomide in humans cannot be ruled out. Therefore, a pregnancy prevention program must be followed.

2.1.1. Definition of Females of Childbearing Potential

A FCBP is a female who: 1) has achieved menarche at some point, 2) has not undergone a hysterectomy or bilateral oophorectomy or 3) has not been naturally postmenopausal (amenorrhea following cancer therapy does not rule out childbearing potential) for at least 24 consecutive months (ie, has had menses at any time in the preceding 24 consecutive months).

2.1.2. Definition of Females Not of Childbearing Potential

Females who do not meet the above definition of FCBP should be classified as FNCPB.

2.2. Counseling

2.2.1. Females of Childbearing Potential

For a FCBP, pomalidomide is contraindicated unless all of the following are met (ie, all FCBP must be counseled concerning the following risks and requirements prior to the start of pomalidomide):

- She understands the potential teratogenic risk to the unborn child
- She understands the need for effective contraception, without interruption, 28 days before starting pomalidomide, throughout the entire duration of pomalidomide, during dose interruptions and for at least 28 days after the last dose of pomalidomide
- She understands and agrees to inform the Investigator if a change or stop of method of contraception is needed
- She must be capable of complying with effective contraceptive measures
- She is informed and understands the potential consequences of pregnancy and the need to notify her study doctor immediately if there is a risk of pregnancy
- She understands the need to commence pomalidomide as soon as it is dispensed following a negative pregnancy test

- She understands and accepts the need to undergo pregnancy testing based on the frequency outlined in this plan (Section 2.4) and in the Informed Consent
- She acknowledges that she understands the hazards pomalidomide can cause to an unborn fetus and the necessary precautions associated with the use of pomalidomide.

The Investigator must ensure that a FCBP:

- Complies with the conditions of the pregnancy prevention plan, including confirmation that she has an adequate level of understanding
- Acknowledges the aforementioned requirements.

2.2.2. Females Not of Childbearing Potential

For a FNCHB, pomalidomide is contraindicated unless all of the following are met (ie, all FNCHB must be counseled concerning the following risks and requirements prior to the start of pomalidomide):

- She acknowledges she understands the hazards pomalidomide can cause to an unborn fetus and the necessary precautions associated with the use of pomalidomide.

2.2.3. Males

The effect of pomalidomide on sperm development is not known and has not been studied. The risk to an unborn baby in females of child bearing potential whose male partner is receiving pomalidomide is unknown at this time. Therefore, male subjects taking pomalidomide must meet the following conditions (ie. all males must be counseled concerning the following risks and requirements prior to the start of pomalidomide):

- Understand the potential teratogenic risk if engaged in sexual activity with a pregnant female or a FCBP
- Understand the need for the use of a condom even if he has had a vasectomy, if engaged in sexual activity with a pregnant female or a FCBP
- Understand the potential teratogenic risk if the subject donates semen or sperm.

2.3. Contraception

2.3.1. Female Subjects of Childbearing Potential

Females of childbearing potential enrolled in this protocol must agree to use two reliable forms of contraception simultaneously or to practice complete abstinence (True abstinence is acceptable when this is in line with the preferred and usual lifestyle of the subject. Periodic abstinence [eg calendar, ovulation, symptothermal or post-ovulation methods] and withdrawal are not acceptable methods of contraception.) from heterosexual contact during the following time periods related to this study: 1) for at least 28 days before starting pomalidomide; 2) while taking pomalidomide; 3) during dose interruptions; and 4) for at least 28 days after the last dose of pomalidomide.

The two methods of reliable contraception must include one highly effective method and one additional effective (barrier) method. If the below contraception methods are not appropriate for the FCBP, she must be referred to a qualified provider of contraception methods to determine the medically effective contraception method appropriate to the subject. The following are examples of highly effective and additional effective methods of contraception:

- Examples of highly effective methods:
 - Intrauterine device (IUD)
 - Hormonal (birth control pills, injections, implants, levonorgestrel-releasing intrauterine system [IUS], medroxyprogesterone acetate depot injections, ovulation inhibitory progesterone-only pills [e.g. desogestrel])
 - Tubal ligation
 - Partner's vasectomy
- Examples of additional effective methods:
 - Male condom
 - Diaphragm
 - Cervical Cap

Because of the increased risk of venous thromboembolism in subjects with multiple myeloma taking pomalidomide and dexamethasone, combined oral contraceptive pills are not recommended. If a subject is currently using combined oral contraception the subject should switch to another one of the highly effective methods listed above. The risk of venous thromboembolism continues for 4 to 6 weeks after discontinuing combined oral contraception. The efficacy of contraceptive steroids may be reduced during co-treatment with dexamethasone.

[Please note, the above highlighted text is applicable for protocols with dexamethasone-containing pomalidomide regimens.]

Implants and levonorgestrel-releasing intrauterine systems are associated with an increased risk of infection at the time of insertion and irregular vaginal bleeding. Prophylactic antibiotics should be considered particularly in subjects with neutropenia.

2.3.2. Male Subjects

Male subjects must practice complete abstinence (true abstinence is acceptable when this is in line with the preferred and usual lifestyle of the subject. Periodic abstinence [e.g. calendar, ovulation, symptothermal or post-ovulation methods] and withdrawal are not acceptable methods of contraception.) or agree to use a condom during sexual contact with a pregnant female or a FCBP while taking pomalidomide, during dose interruptions and for at least 28 days after the last dose of pomalidomide, even if he has undergone a successful vasectomy.

2.4. Pregnancy Testing

Medically supervised pregnancy tests with a minimum sensitivity of 25 mIU/mL must be performed for FCBP.

Females of childbearing potential must have two negative pregnancy tests (sensitivity of at least 25 mIU/mL) prior to starting pomalidomide. The first pregnancy test must be performed within 10 to 14 days prior to the start of pomalidomide and the second pregnancy test must be performed within 24 hours prior to the start of pomalidomide. The subject may not receive pomalidomide until the study doctor has verified that the results of these pregnancy tests are negative.

Females of childbearing potential with regular or no menstrual cycles must agree to have pregnancy tests weekly for the first 28 days of study participation and then every 28 days while taking pomalidomide, at study discontinuation, and at Day 28 following the last dose of pomalidomide.

Females of childbearing potential with irregular menstrual cycles must agree to have pregnancy tests weekly for the first 28 days of study participation and then every 14 days while taking pomalidomide, at study discontinuation, and at Days 14 and 28 following the last dose of pomalidomide.

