For all subjects who enroll into this study, study visits and serial measurements of safety and efficacy will be performed as outlined in Table 1, Table of Events. The overall study design is depicted in Figure 1.

[figure not shown]

Figure 1: Overall study design

Table 1: Table of events

	SCREENING	CYCLE 1					CYCLE 2+					END OF TREATMENT	FOLLOW UP
PROCEDURE	Day -28 to -1	Days -2, -1 (+/- 10 days)	Day 1 (+/- 10 days)	Day 8 (+/- 10 days)	Day 15 (+/- 10 days)	Day 22 (+/- 10 days)	Days -2, -1 (+/- 10 days)	Day 1 (+/- 10 days)	Day 8 (+/- 10 days)	Day 15 (+/- 10 days)	Day 22 (+/- 10 days)	28 days after last dose (+/- 28 days)	Q3 Months (+/- 28 days)
Informed Consent	X												
Inclusion/Exclusion Criteria	X												
Medical/Treatment History	X												
Vital Signs ^h	X	X	X	X	X		X	X	X	X	X	X	
Physical Exam	X	X	X	X	X		X	X	X	X	X	X	
Neurologic Exam	X		X					X					
Weight	X		X					X				X	
ECOG	X												
Patient reported outcomes – Quality of Life (QoL)	X		X					X				X	
PFT/FEV1 testing for patients with history of COPD/persistent asthma	X												
AE/SAE review		Continuous											
Medication evaluation	X	Continuous											
LOCAL LABS													
Venipuncture (Facility Fee)	X												
CBC (w/ platelet count)	X	X	X	X	X	X	X	X	X	X	X	X	
Serum Chemistry	X	X	X	X	X	X	X	X		X		X	
Hepatitis B (HBV) serology ^e	X												
HBV DNA testing ^f	X	Q12W during treatment, at the End of Treatment Visit, and Q12W for up to 6 months after the last dose of study treatment											
TSH, T3, Free T4, Coagulation	X												

	SCREENING	CYCLE 1					CYCLE 2+					END OF TREATMENT	FOLLOW UP
PROCEDURE	Day -28 to -1	Days -2, -1 (+/- 10 days)	Day 1 (+/- 10 days)	Day 8 (+/- 10 days)	Day 15 (+/- 10 days)	Day 22 (+/- 10 days)	Days -2, -1 (+/- 10 days)	Day 1 (+/- 10 days)	Day 8 (+/- 10 days)	Day 15 (+/- 10 days)	Day 22 (+/- 10 days)	28 days after last dose (+/- 28 days)	Q3 Months (+/- 28 days)
Thiamine testing	X		X					X					
Urinalysis	X												
Pregnancy Test	X		X					X					
Triglycerides	X		X	X	X	X		X	X	X	X		X
SPEP, UPEP, Serum/Urine Immunofix., Quant IgGs, 24Hr Urine, SFLC, B2 Micro	SOC		X					X					
CORRELATIVE SAMPLING													
Correlative Studies – peripheral blood collection, stool samples	X ^{b,d}	X ^{b,d}	X ^{b,d}					X ^{c,d}				X ^{c,d}	X ^{c,d}
Correlative Studies – bone marrow	X ^b	X ^b	X ^b									X	X ^c
CARDIOLOGY, PATHOLOGY, RADIOLOGY													
12-lead ECG	X ^g	X		X	X	X	X						
ECHO	X												

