3. POMALIDOMIDE EDUCATION AND COUNSELING GUIDANCE DOCUMENT FOR FEMALE SUBJECTS

To be completed prior to each dispensing of pomalidomide.

Protocol Number:

Subject Name (Print): _____ DOB: _____ / _____ / _____ (dd/mmm/yyyy)

Check one risk category:

- FCBP (Female of childbearing potential): a female who: 1) has achieved menarche (first menstrual cycle) at some point, 2) has not undergone a hysterectomy (the surgical removal of the uterus) or bilateral oophorectomy (the surgical removal of both ovaries) or 3) has not been naturally postmenopausal (amenorrhea following cancer therapy does not rule out childbearing potential) for at least 24 consecutive months (i.e. has had menses at any time during the preceding 24 consecutive months)
- NOT FCBP

3.1. Female of Childbearing Potential:

1. I have verified and counseled the subject regarding the following:

- Potential risk of fetal exposure to pomalidomide: A teratogenic potential of pomalidomide in humans cannot be ruled out. If pomalidomide is taken during pregnancy, it may cause birth defects or death to any unborn baby. Females are advised to avoid pregnancy while taking pomalidomide. Females of childbearing potential must agree not to become pregnant while taking pomalidomide.
- That the required pregnancy tests performed are negative.
- The subject confirmed that she is using TWO reliable methods of birth control at the same time, or complete abstinence (True abstinence is acceptable when this is in line with the preferred and usual lifestyle of the subject. Periodic abstinence [e.g. calendar, ovulation, symptothermal or post-ovulation methods] and withdrawal are not acceptable methods of contraception.) from heterosexual contact (at least 28 days prior to receiving pomalidomide, while receiving pomalidomide, during dose interruptions and for at least 28 days after the last dose of pomalidomide).

One highly effective method and one additional method of birth control must be used AT THE SAME TIME. The following are examples of highly effective and additional effective methods of contraception:

- Examples of highly effective methods:
 - Intrauterine device (IUD)
 - Hormonal (birth control pills, injections, implants, levonorgestrel-releasing intrauterine system [IUS], medroxyprogesterone acetate depot injections, ovulation inhibitory progesterone-only pills [e.g. desogestrel])

- Tubal ligation
 - Partner's vasectomy
 - Examples of additional effective methods:
 - Male condom
 - Diaphragm

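### Table 1 leaves unmarked several pregnancy tests that Appendix C requires, and inclusion criteria 10 to 12 are looser than Appendix C on childbearing status, first-test timing and condoms after vasectomy

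*Combined protocol and SAP*

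**What the plan says.** Section 4.1 keeps all subjects on the pomalidomide pregnancy prevention plan throughout the study. It cites the plan as Appendix D, but the plan is Appendix C. Appendix C, Section 1, applies the plan to every trial subject receiving pomalidomide.

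For women of childbearing potential with regular or no cycles, Appendix C 2.4 requires "pregnancy tests weekly for the first 28 days of study participation and then every 28 days while taking pomalidomide, at study discontinuation", and then at Day 28 after the last dose. With irregular cycles the weekly tests are the same, followed by tests "every 14 days while taking pomalidomide, at study discontinuation, and at Days 14 and 28 following the last dose of pomalidomide". Before treatment there are two tests: "The first pregnancy test must be performed within 10 to 14 days prior to the start of pomalidomide", and the second falls within the preceding 24 hours. Section 2.5.2.1 repeats the on-treatment and post-treatment schedule.

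Section 4.1 also refers sites to Table 1 for serial safety and efficacy measurements. There the "Pregnancy Test" row is marked in 3 of 13 visit columns: screening, Cycle 1 Day 1, and Day 1 of Cycle 2 onward. No footnote adds tests. In-cycle visits carry a window of +/- 10 days. The end-of-treatment column is timed "28 days after last dose (+/- 28 days", without saying of which drug.

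Inclusion criteria 10 to 12 (Section 6.2, repeated in the Protocol Summary) set their own rules on childbearing status, pregnancy testing at entry and male contraception.

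**The concern.** One protocol gives sites two schedules for the same safeguard. Neither Section 4.1 nor Section 6.2 says which text prevails where they differ, and the one cross-reference to the plan carries the wrong appendix letter. A site that builds its visits from Table 1 and screens from Section 6.2 would be working to the looser version of both.

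What is at stake is participant and fetal safety, not inference. Appendix C 2.1 describes pomalidomide as a thalidomide analogue, teratogenic in two animal species, and makes a prevention programme mandatory for that reason.

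**Working it through.** The plan states no total number of tests, so there is no figure to reproduce. The check has four parts.

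**1. Count of tests.** Let k be the number of 28-day cycles. Section 4.1 plans at least 8, conditional on no progression or unacceptable toxicity, so k can be anything from 1. Assumptions: the first 28 days run from Cycle 1 Day 1, and the Day 1 test serves both as the 24-hour pre-start test and as the first weekly test. The second assumption favours Table 1.

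- Table 1: 1 (screening) + k (Day 1 of each cycle) = k + 1.
- Appendix C, regular or no cycles: 1 (first pre-start) + 4 (weekly in Cycle 1) + (k - 1) + 1 (discontinuation) + 1 (Day 28) = k + 6. Shortfall: (k + 6) - (k + 1) = 5 for every k.
- Appendix C, irregular cycles: 1 + 4 + 2(k - 1) + 1 + 2 (Days 14 and 28) = 2k + 6. Shortfall: (2k + 6) - (k + 1) = k + 5.

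| | Required | Marked | Unmarked |
|---|---|---|---|
| Regular, k = 1 | 7 | 2 | 5 |
| Regular, k = 8 | 14 | 9 | 5 |
| Irregular, k = 1 | 8 | 2 | 6 |
| Irregular, k = 8 | 22 | 9 | 13 |

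If the discontinuation test coincides with another, subtract 1: 4 with regular cycles, 5 to 12 with irregular.

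The unmarked tests are Cycle 1 Days 8, 15 and 22; the mid-cycle test from Cycle 2 on (irregular cycles); discontinuation; and Day 28 (also Day 14 if irregular) after the last pomalidomide dose. The blanks are not an artefact of a damaged table. The blood-count row, "CBC (w/ platelet count", is marked at Days 8, 15 and 22 and at end of treatment.

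**2. Which unmarked tests meet a later check.** Assume one dispensing per cycle, on Day 1 (Appendix C 2.5.3 caps each supply at 28 days), with a counselling form at each.

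- k = 1: all 5 (regular) or 6 (irregular) fall after the only dispensing.
- k of 2 or more, regular: discontinuation and Day 28, so 2 fall after the last dispensing. The other 5 - 2 = 3 precede a later form.
- k of 2 or more, irregular: the last mid-cycle test, discontinuation, and Days 14 and 28, so 4. The other (k + 5) - 4 = k + 1 precede a later form, which is 9 at k = 8.

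**3. Timing.** With +/- 10 days on each visit, two visits nominally 7 days apart could be 7 + 10 + 10 = 27 days apart. The end-of-treatment window is 28 +/- 28, or days 0 to 56 after an unnamed last dose. Pomalidomide runs to Day 21 of a cycle, while daratumumab may fall last on Day 1, 15 or 22. Table 4 also allows pomalidomide alone to be stopped. The end-of-treatment visit therefore cannot be taken as Day 28 after the last pomalidomide dose.

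**4. Eligibility text beside Appendix C.**

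| Item | Section 6.2 | Appendix C |
|---|---|---|
| First test (criterion 11) | Any time in the 28 days before first dose | 10 to 14 days before pomalidomide (2.4) |
| Menopause (criterion 10) | Over 45 with 12 months' amenorrhea, or 6 months plus FSH >40 at any age | 24 consecutive months of natural menopause; amenorrhea after cancer therapy does not count (2.1.1) |
| Surgery (criterion 10) | Also accepts tubal occlusion and salpingectomy | Hysterectomy or bilateral oophorectomy only (2.1.1) |
| Vasectomised men (criterion 12) | No barrier asked for | Condom or complete abstinence regardless (2.3.2) |

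Each difference runs the same way: Section 6.2 is looser. The cancer-therapy clause matters here because criterion 2 requires at least two prior lines of treatment.

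**The case against.** The strongest reply is that Appendix C enforces itself. Under 2.2.1, pomalidomide is contraindicated for a woman of childbearing potential unless she accepts testing at the 2.4 frequency, and the investigator must ensure that she complies with the plan. Section 2.5.2.1 restates the schedule, asks for contraception to be confirmed at each visit, requires counselling at least every 28 days, and stops the drug for evaluation after a missed period. Under 2.4, "The subject may not receive pomalidomide until the study doctor has verified that the results of these pregnancy tests are negative". A signed form, "To be completed prior to each dispensing of pomalidomide", repeats the 24-month definition and the full schedule and asks the counsellor to verify negative tests. The male form asks about condoms, including after vasectomy. Section 2.2.1 also relies on the informed consent, which was not available for this review, so Table 1 may not be the only other schedule that sites hold.

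Most of this stands. A mistimed first test should lead to delay or a retest, not to exposure. The eligibility rules can be met together with the plan: a test at 10 to 14 days satisfies both, and a vasectomised man can comply with both. Appendix C 2.3.1 lists tubal ligation as a highly effective method, so such women remain within the plan's contraception rules. With two or more cycles, a later form would meet every missing Cycle 1 weekly test and all but the last mid-cycle test.

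Two things survive. A later form can reveal an omission only after the test was due, and no later form follows the last dispensing. And Table 1 and Section 6.2 still direct sites to something less than the plan requires.

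**Conclusion.** The inconsistency is real. Table 1 leaves 5 required tests unmarked with regular or no cycles, and 6 (one cycle) to 13 (eight cycles) with irregular cycles, each less 1 if the discontinuation test coincides with another. Criteria 10 to 12 are looser than the plan on three matters. A site working from Table 1 and Section 6.2 alone could miss mandatory tests or misclassify women. The least protected tests are those after the last dispensing: 2 (regular) or 4 (irregular) with two or more cycles, and all 5 or 6 with one cycle, before any such overlap. The counts rest on the Day 1 and once-per-cycle dispensing assumptions stated above.

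Three stronger readings are not supported:

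- A reader might infer that sites would necessarily breach the plan, or that fetal exposure would follow. Section 4.1 and Appendix C are operative text too, and the controls in 2.2.1, 2.4 and 2.5.2.1 stand between a blank cell and a missed test.
- A reader might take 5 to 13 as the number of unprotected tests. It is the number of tests without a mark in Table 1; many meet a later form.
- A reader might infer that existing visits cover nearly all the missing tests, counting end of treatment as Day 28. Table 1 does not say which drug's last dose it means.

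No statistical property of the design is affected. The number of women concerned is not stated and may be small.

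**What to change.** - In Sections 4.1 and 6.2, state that Appendix C governs pregnancy prevention wherever it is stricter, and correct the Appendix D citation to Appendix C.
- In Table 1, mark the pregnancy test at Cycle 1 Days 8, 15 and 22, at discontinuation, and at Day 28 after the last pomalidomide dose. Add a footnote for irregular cycles: Day 15 of later cycles and Day 14 after the last pomalidomide dose.
- Anchor the post-treatment tests to the last pomalidomide dose, and exempt all these tests from the +/- 10-day and +/- 28-day windows.
- Align criteria 10 to 12, in Section 6.2 and the Protocol Summary, with Appendix C on childbearing definition, first-test timing and condoms regardless of vasectomy. Keep body text that is stricter, such as 3 months without sperm donation against 28 days in Appendix C 2.5.2.2.

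The cost is a wording amendment and a table edit. No test is added beyond what Appendix C already requires. The in-cycle tests fall on visits that Table 1 already has. The post-treatment tests may need their own dates once tied to pomalidomide, and Day 14 after the last dose has no visit at present.
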